2. OBJECTIVES

Primary objective:

Comparison of the hemoglobin level 3 and 6 weeks postoperatively between the different groups

Secondary objectives:

- Comparison of quality of life after 1, 3 and 6 weeks postoperatively between the different groups
- Comparison of the side-effects of various drugs
- Is there a “subgroup” of patients who have the greatest effect of the medication used (eg patients with low ferritin)
- Is there a “subgroup” of patients who respond better to ferinject than ferrous fumarate and vice versa (eg patients with elevated CRP).
- What are the costs of taking oral iron or intravenous iron

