7.1.2 Secondary study parameters

- Quality of life after 1, 3 and 6 weeks
- Side effects of medication
- Predictive value of other parameters such as CRP, transferrin, ferritin and hepcidin
- Cost analysis

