9. STATISTICAL ANALYSIS

9.1 Primary study parameter

Primary study parameter is change in hemoglobin level (mmol/L) between baseline and either 3 or 6 weeks postoperatively. Differences in change between the two experimental groups, and between each experimental group and the control group will be tested by use of the Student's T-test.

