9.4 Secondary study parameters

Quality of life

Each patient will be asked to complete three questionnaires at four times: at baseline after informed consent before starting iron treatment, and 1, 3 and 6 weeks postoperatively. The questionnaires are: 1) the EuroQoL, a generic health related quality of life questionnaire. In this questionnaire patients indicate their current health in five dimensions: mobility, self-care, usual activities, pain/discomfort, and anxiety/depression 2) the Multi-Dimensional Fatigue Questionnaire which is a 20-item self-reported instrument to measure fatigue. At baseline (first day postoperatively in the hospital but before the study-medication is started) patients will be asked to complete the questionnaires. At 1 week after start of the treatment, the research nurse will call the patient at home to ask whether the second questionnaire has been completed. After 3 weeks the nurse visits the patient and will ensure that the questionnaires about the quality of life after 1 and 3 weeks are completed. At 6 weeks, the patient will visit the outpatient clinic and will also be seen by the research nurse who will check whether the last questionnaire has also been completed.

Quality of life data between the groups will be analysed using Repeated Measurement

ANOVA.

Side effects of the medication

The next side effects will be registered: headache, constipation, diarrhea, nausea, dizziness, rash and stomach-ache. On questionnaire B, C, and D the patients can indicate whether there is any of these side effects.

For each potential side effect, the percentage of patients reporting it will be compared between groups. Groups will be compared using the Chi-square test.

Predictive value of other parameters

We will determine for number of parameters whether they predict patients' sensitivity to iron supplementation. These parameters are: CRP, transferrin, ferritin and hepcidin. The significance of these parameters will be determined by doing subgroup analyses among patients with either high or low values of the parameters (i.e. the similar analyses as in 9.1 but within subgroups).

Cost-analysis

Resource use and costs of the intravenous and oral iron therapy will be measured. If relevant and appropriate, a cost-minimisation or a cost-effectiveness analysis will be performed. In that case, the analysis will include a time-horizon of 6 weeks and be performed from a health care perspective.

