Annex 1. Assessment schedule

Visits and Timepoints ¹	Pre-operative	Surgery	Post-operative	Week 1	Week 3	Week 6	Withdrawal
	Screening			Telephone call	Home visit		
Assessments	Day - 3 to -1	Day 0	Day 1, within 24-48 hours after surgery	Day 7	Day 21	Day 42	
Informed consent	X						
Inclusion/exclusion criteria	X						
Demography (age, race)	X ²						
Relevant Medical History / Current medical conditions	X ²						
ASA score	X ²						
Type of surgery		X ²					
Amount of blood loss during surgery		X ²					
Hb	X		X		X	X	
Transferrin, Ferritin, CRP	X		X ²		X	X	
Hepcidin	X		X ²		X	X	
QoL questionnaires			X ²	X	X	X	
(Serious) Adverse events			X ²	X	X	X	X
Randomization			X ²				
Dispense studymedication			X ²				
Drug accountability			X ²		X	X	X
Collect not-used study medication						X	X
¹ Due to logistic reasons adjustments in timepoints can occur							
² Only if post-operative Hb is within 5 and 7 mmol/L

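### Section 9.4 judges four continuous markers as predictors of response only by t-tests in undefined high and low subgroups; a continuous arm-by-marker model is the better main analysis unless a threshold is known

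*Combined protocol and SAP*

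**What the plan says.** Section 7.1.2 lists as a secondary parameter "Predictive value of other parameters such as CRP, transferrin, ferritin and hepcidin". Section 2 puts the aim as a question about "patients who have the greatest effect of the medication used (eg patients with low ferritin"), and adds a second question about who does better on one iron product than the other, with raised CRP as the example. No cut-off is attached to either example.

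Section 9.4 sets out to determine for each marker "whether they predict patients' sensitivity to iron supplementation", and states the method as "subgroup analyses among patients with either high or low values of the parameters (i.e. the similar analyses as in 9.1 but within subgroups"). Section 9.1 compares change in hemoglobin from baseline to 3 or 6 weeks between the two iron groups; differences "between each experimental group and the control group will be tested by use of the Student's T-test".

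No other analysis of the markers is planned. The linear regression in section 9.3 is reserved for prognostic imbalance between arms at baseline. Annex 1 schedules the markers pre-operatively, on day 1 and at weeks 3 and 6. Section 9.4 does not say which of these measurements defines high and low.

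**The concern.** All four markers are laboratory measurements on a continuous scale. Cutting each in two treats a woman just above the cut like one far above it, and as the opposite of one just below it. The answer then depends on a cut that nobody has fixed.

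Whether a marker predicts sensitivity to iron is a question about a difference between treatment effects. Separate t-tests within each half do not address it. One half can reach significance and the other miss it when the two effects are equal.

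The Introduction asks whether hemoglobin alone is enough to decide on iron or whether other blood values are needed, and the marker analysis is the part of the trial that speaks to this. The risk is that a useful marker is reported as useless, or the reverse, from samples already taken and paid for.

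**Working it through.** **Inputs.** From section 4.4: clinically important difference 0.5 mmol/L, SD 0.7 mmol/L, power 80%, 32 per group, 120 in total (40 per arm if equal). From section 9.5: two-sided 5%. Assumptions of mine: the marker is normal (after a log transformation where needed), one pairwise contrast is examined, and 0.7 is the residual SD. The *gap* is the treatment effect in the upper half of the marker minus that in the lower half. The plan gives no gap. I use its 0.5 as one value; 0.3, 0.7 and 0.8 are purely assumed.

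**1. The plan's own figure.** n = 2 × (1.960 + 0.842)² × 0.7² / 0.5² = 30.8, so 31 per group. The t-based solution is 31.8, so 32. Then 3 × 32 = 96, and 96 / 0.80 = 120. The stated size reproduces.

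**2. Information kept by a split.** For a normal marker with a linear effect, a cut at quantile p keeps φ(z_p)² / [p(1 − p)]. At the median this is 0.399² / 0.25 = 0.637, a loss of 36%. The loss is 41% at 33/67, 46% at 25/75 and 51% at 20/80.

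**3. Closed-form check, 32 per arm, gap 0.5.** A median split gives four cells of 16, so the standard error of the interaction is √(4 × 0.49 / 16) = 0.35. The ratio is 0.5 / 0.35 = 1.43 and the power is Φ(1.43 − 1.96) = 30%. Keeping the marker continuous raises the ratio to 1.43 / √0.637 = 1.79, with power Φ(1.79 − 1.96) = 43%. At 40 per arm the same steps give 36% and 52%.

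**4. Simulation.** Hemoglobin outcome = 0.5 × arm + β × arm × marker + error, with error SD 0.7 and β = gap / (2 × 0.798). The test is the least-squares interaction test, on 20,000 trials per setting. Rejection with no interaction is about 5% for both versions. Power, continuous vs median split:

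| Gap (mmol/L) | 32 per arm | 40 per arm |
|---|---|---|
| 0.3 | 18% vs 13% | 21% vs 15% |
| 0.5 | 40% vs 27% | 48% vs 33% |
| 0.7 | 66% vs 45% | 77% vs 55% |
| 0.8 | 77% vs 56% | 86% vs 66% |

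These run a few points below step 3 because t quantiles are used and the marker varies between arms. Repeat runs move a figure by about a point, so I quote losses of 5 to 6, 12 to 15, and 19 to 22 points.

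**5. Other shapes.** If the effect jumps exactly at the median cut, power for continuous vs split at 32 per arm is 20% vs 29% (jump 0.5), 33% vs 50% (0.7) and 41% vs 61% (0.8). At 40 per arm it is 23% vs 35%, 41% vs 60% and 49% vs 71%. The split gains about 9 to 22 points. If the jump lies at the 75th percentile while the cut is at the median, the results at 32 per arm are 14% vs 10%, 22% vs 15% and 27% vs 18%. At 40 per arm they are 16% vs 12%, 27% vs 18% and 33% vs 22%. The continuous model gains about 4 to 11 points.

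**6. The analysis actually planned.** Within one half, the t-test has 50% power for 0.5 mmol/L with 16 per arm and 60% with 20. If the true effect is 0.5 in both halves, exactly one half is significant with probability 2 × 0.50 × 0.50 = 50%, or 2 × 0.60 × 0.40 = 48%. About half of such trials would suggest prediction by a marker that predicts nothing.

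**The case against.** The objectives ask about subgroups, with low ferritin and raised CRP as examples, and a high/low analysis answers in those terms. The Introduction does not describe a graded effect either. It speaks largely in states: normal iron stores, iron deficiency before surgery, a block on iron mobilisation from inflammation. If a real threshold sat at the cut, the split would be the stronger test, by about as much as it loses under linearity.

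The power comparison also sets one interaction test against another, and section 9.4 contains neither. At a gap of 0.3 the loss is small. At 0.5 even the continuous test has only 40% to 48% power, so a null result would stay inconclusive.

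All of this stands as a limit on the size of the point. It does not rescue the plan as written. A threshold argument needs a threshold, and none is stated. A jump away from the chosen cut favours the continuous model. The subgroup wording of the objectives can be met by reading the fitted treatment difference at low and high marker values.

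**Conclusion.** The point holds as a limited one. Section 9.4 leaves the marker question to within-subgroup t-tests with no cut-off, no marker time point and no treatment-by-marker test, and nothing elsewhere repairs this. Under a roughly linear effect on the (log) marker, a median split loses about 36% of the information. In interaction tests that is about 5 to 22 points of power for gaps of 0.3 to 0.8 mmol/L. A threshold exactly at the cut reverses the comparison.

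Three stronger readings are tempting and not supported:

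- That the plan forfeits this much power as it stands. The figures describe a split interaction test, which it does not propose; the lack of any such test is the more basic gap.
- That a graded effect is established. The documents settle neither shape.
- That a median split is planned. It is assumed here only to size the loss.

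The analysis is secondary, and the primary test and sample size do not depend on it.

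**What to change.** In section 9.4, make the main analysis for each marker a linear regression of hemoglobin at 3 weeks (the time point of section 4.4), with 6 weeks reported likewise. The terms are:

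- treatment arm;
- the marker as a continuous variable, on the log scale for CRP, ferritin and hepcidin;
- arm-by-marker;
- baseline hemoglobin.

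Name in advance which pre-treatment measurement is used, pre-operative or day 1, so that a value affected by treatment cannot serve as the predictor. Report the interaction, and the treatment difference with its 95% CI across the marker range. Keep high and low subgroup means as description only, with the cut stated.

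This costs a few sentences and a little analysis time, with no extra patients, samples or assays. The model assumes approximate linearity, loses power if there is a true threshold at the cut, and gives no direct cut-off for practice, although the effect can be read off at any marker value.

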9.5 Alpha

We will employ an alpha of 5% (2-sided testing).

9.6 Handling of missing values

Missing values in the primary outcome parameter (hemoglobin) will be imputed by means of the last known observation. Missing values in baseline characteristics will be imputed by means of a multiple imputation procedure.

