3. STUDY DESIGN

The study will be a double blind randomized controlled trial.

Patients undergoing a primary caesarean section in the Maastricht University Medical Centre and the Orbis Medical Centre in Sittard will be informed about the study, both in writing and orally. A schematic overview of assessments is given in the schedule at the end of the protocol (annex 1).

If the patient has signed the informed consent the patient data will be entered in a database and then the pre-operative blood will be taken (standard and extra). If the postoperative hemoglobin level is between 5-7 mmol/L the patient will be randomized and two extra blood tubes will be taken. Randomization will be done by the computer and the first questionnaire will be completed. The patient characteristics will be copied from the electronic patient record. Subsequently, each patient will receive an infusion with a placebo or with Ferinject[®] (depending on which group the patient ended up). The patients will not know the actual treatment, because the infusion line and the flask with NaCl or Ferinject[®] will be packed. Also the venflon will be covered by a gauze. So both the patient and the doctor will not know if a placebo or the Ferinject[®] itself is given. The patient will receive 60 capsules to take home, which need to be taken two times daily. This can be ferrous fumarate or a placebo. To verify compliance, patients will use a dispenser which count how often it is opened. Postoperatively, the hemoglobin will be determined another two times: after 3 and 6 weeks. At 3 weeks the research nurse will do this at the patient's home and the second time this will be obtained in the hospital where it can be combined with the regular control. The research nurse will call the patient after 1 week to ask how things are going and whether the second questionnaire has been completed. If the nurse visits the patient after 3 weeks, she will ensure that the questionnaires about the quality of life after 1 and 3 weeks were completed. The day the patient will come for the regular check at 6 weeks, she will also be seen by the research nurse who will check whether the last questionnaire was also completed. At this appointment the hemoglobin and other blood-values will also be determined.

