4.4 Sample size calculation

This study will examine whether intravenous iron gives an improvement of the hemoglobin content 3 weeks postoperatively in patients with a hemoglobin between 5-7 mmol / L after caesarean sections, compared with giving oral iron, as well as placebo.

Based on the assumption that a minimum of 0,5 mmol/L difference in the hemoglobin level is thought to be of clinical importance and a standard deviation of 0,7 mmol/L (based on a retrospective analysis and a comparable study ⁴) it was determined that, with an alpha of 5% and a power of 80%, for each group 32 patients are needed. For 3 groups this means 96 patients. Allowing for patients lost to follow-up, the study number was set on 120 patients to guarantee adequate numbers of patients in each group.

A retrospective analysis performed at the Maastricht University Medical Centre between 1 January 2015 and June 30 2015, showed that 66 patients had a primary caesarean section. If we exclude the patients that had an operation on Friday (because during the weekends the study-medication cannot be prepared) the remaining number were 46 patients. Of these 46 patients, 31 people had a hemoglobin level between 5.0 and 7.0 mmol / L. If we assume that 70% of patients want to participate in the study, this will lead to 44 patients per year to randomize at the MUMC⁺. The other participating hospital (Zuyderland Sittard-Heerlen) has a double amount of deliveries including Caesarean sections which means that we need at maximum 1,5 year to complete the study.

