7.3 Study procedures

Interventions

Blood

Postoperative determination of the hemoglobin level is part of the regular care and will be performed on the first day after the operation.

In this study we want to examine the blood three times more than in the regular care, namely 1 day and 3 and 6 weeks postoperatively. At 1 day (after randomization and before treatment) it will be taken in the hospital. At 3 weeks the research nurse will visit the patient at home. At 6 weeks the patient will visit the hospital for the regular follow up.

Determination of other parameters in the blood will not lead to more discomfort of the patient.

The lab results will be saved using an anonymous survey number.

Administration of an infusion

Each patient has postoperative IV, so no extra IV is needed for the study. The patient will receive either a flask NaCl (placebo) or a single dose of Ferinject[®] on the first or second day after the operation (24-48 hours postoperatively).

Capsules

The patient will start using capsules (either a placebo or ferrous fumarate) on the first or second day after the operation (24-48 hours postoperatively).

Each patient is given 60 capsules to take home, where she has to take 1 capsule 2 times a day.

Questionnaire

Each patient will be asked to complete a questionnaire four times: after informed consent before starting treatment, and 1, 3 and 6 weeks postoperatively. This questionnaire is a combination of the EuroHRQoL and MFI questionnaires. Completing the questionnaire takes about 10-20 minutes and can be filled in via computer or on paper.

This will be conducted as follows: the first questionnaire will be completed in the hospital the first day postoperatively before the study-medication is started. After 1 week the research nurse will call the patient at home to ask how things are going and whether the second questionnaire has been completed. After 3 weeks the nurse visits the patient and will ensure that the questionnaires about the quality of life after 1 and 3 weeks are completed. The day the patient will come for the regular check at 6 weeks, she will also be seen by the research nurse who will check whether the last questionnaire has also been completed.

Data collection

Patient characteristics. The following information will recorded:

- Age
- Morbidity

- Race
- ASA score
- Use of iron therapy preoperative (doses and duration of iron therapy)
- Amount of blood loss during surgery

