7.5 Replacement of subjects in case of withdrawal

A dropout of 10-20% is taken into account. Results will still be included, unless the patient withdraws consent. Assessments that will be done at the withdrawal visit are adverse events, drug accountability and collect not-used study medication.

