9.3 Multivariable analysis

In case of prognostically important baseline differences between groups, multivariable linear regression analysis will be carried out instead of the Student's T-test.

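### Imputing missing hemoglobin by the last known value scores a woman with no week-3 sample at her pre-treatment level, which distorts the week-3 difference and can take power below 80%

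*Combined protocol and SAP*

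**What the plan says.** - **Outcome and test.** Section 9.1: "Primary study parameter is change in hemoglobin level (mmol/L) between baseline and either 3 or 6 weeks postoperatively". Arms are compared in pairs by Student's t-test. Section 9.1 does not say whether baseline is the preoperative or the day-1 sample.
- **Missing hemoglobin.** Section 9.6: "Missing values in the primary outcome parameter (hemoglobin) will be imputed by means of the last known observation". No sensitivity analysis for missing hemoglobin appears anywhere in the document. For baseline variables the same section uses a different method: "Missing values in baseline characteristics will be imputed by means of a multiple imputation procedure".
- **Sampling times.** Section 7.3 on the postoperative study sample: "At 1 day (after randomization and before treatment) it will be taken in the hospital". Section 3 on what follows: "Postoperatively, the hemoglobin will be determined another two times: after 3 and 6 weeks". In Annex 1 the week-1 contact is a telephone call with no blood sample.
- **Women who leave.** Section 7.5: "A dropout of 10-20% is taken into account. Results will still be included, unless the patient withdraws consent".
- **Sample size.** Section 4.4 frames its question at 3 weeks and finds 32 per group, 96 in all. It then adds: "Allowing for patients lost to follow-up, the study number was set on 120 patients to guarantee adequate numbers of patients in each group".
- **Regression alternative.** Section 9.3: "In case of prognostically important baseline differences between groups, multivariable linear regression analysis will be carried out". This concerns baseline imbalance and does not change how missing outcomes are handled.

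**The concern.** At week 3 the last available hemoglobin is always a pre-treatment one. A woman without a week-3 sample is entered as though neither treatment nor natural recovery had altered her hemoglobin, and the t-test treats that value as observed. On the ordinary reading of carrying the last value forward, this applies even if her week-6 value was measured.

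Three consequences follow at the time point on which the trial was sized:

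1. The difference is pulled toward zero when loss is equal between arms.
2. When hemoglobin rises generally and loss is unequal, the difference can be enlarged or reduced, and one can appear where none exists. The rule is therefore not reliably conservative.
3. The allowance for dropout assumes that lost women contribute nothing. Under this rule they contribute diluting values, so the stated 80% power does not describe the planned analysis.

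**Working it through.** **Inputs from the document.** Difference 0.5 mmol/L, SD 0.7, two-sided alpha 5%, power 80%, 32 per group, 120 randomised (sections 4.4 and 9.5); equal allocation is implied, giving 40 per arm. Dropout 10-20% (section 7.5).

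**Assumptions, not in the document.** The SD of 0.7 applies to change among observed women. Baseline is day 1. All loss falls before week 3 and none is by withdrawal of consent. The comparator's mean rise to week 3 is m = 0, 0.5, 1.0 or 1.5 mmol/L; the intravenous arm rises by m + 0.5.

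**The plan's own figure.** The two-sample t-test calculation gives 31.76, so 32 per group. 3 × 32 = 96, and 96 / 0.80 = 120. Both are reproduced. With observed values only, power is 88.4% with 40 per arm, 84.8% with 36 (10% loss) and 80.3% with 32 (20% loss). The inflation is right for an observed-data analysis.

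**Equal loss, fraction q imputed in each arm.**

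- Estimated difference = (1 − q)(m + 0.5) − (1 − q)m = 0.5(1 − q). This is 0.45 at q = 0.10 and 0.40 at q = 0.20, whatever m is.
- Arm variance = (1 − q) × 0.49 + q(1 − q) × (arm mean rise)².
- Example, q = 0.20, m = 1.0. Comparator: 0.392 + 0.16 × 1.00 = 0.552. Intravenous: 0.392 + 0.16 × 2.25 = 0.752. Standard error = √(1.304 / 40) = 0.181. The ratio 0.40 / 0.181 = 2.2 gives 59% power.

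Noncentral-t power, 40 per arm:

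| Loss before week 3 | Estimate | m = 0 | m = 0.5 | m = 1.0 | m = 1.5 |
|---|---|---|---|---|---|
| 5% | 0.475 | 86.3% | 84.6% | 81.3% | 76.4% |
| 10% | 0.45 | 84.0% | 80.5% | 73.7% | 64.8% |
| 20% | 0.40 | 78.6% | 71.2% | 59.0% | 46.5% |

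Power drops below 80% once early loss exceeds roughly 17.6%, 10.5%, 5.8% and 3.5% for the four rises. Simulation with random loss agrees to within one percentage point at 10% and 20%.

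**Milder patterns of loss.**

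- If half of a 20% loss is by withdrawn consent, 36 per arm are analysed with 4 imputed: estimate 0.5 × 32/36 = 0.44, power 79.4%, 75.1%, 67.3% and 57.8%.
- If all of it is by withdrawn consent, nothing is imputed and power is 80.3%.
- If half of it comes after week 3, the 10% row applies at week 3.

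**Unequal loss (assumed 10% against 20%).** Estimate = (1 − q_IV)(m + 0.5) − (1 − q_C)m. With m = 1.0:

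- Comparator loses more: 0.90 × 1.5 − 0.80 × 1.0 = 0.55.
- Intravenous arm loses more: 0.80 × 1.5 − 0.90 × 1.0 = 0.30.

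With no true effect the spurious difference is (q_C − q_IV)m, which is 0.05, 0.10 or 0.15 for m = 0.5, 1.0 or 1.5. Simulated type I error is then 6.3%, 9.3% and 12.5% against a nominal 5%.

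**The case against.** The strongest objection is that the power losses rest on inputs the document does not supply. The comparator rise and the timing of loss are unknown, and a nurse visits at home for the week-3 sample, which makes early loss less likely. The power loss is modest or absent at 5% loss for rises up to 1.0, and at 10% for rises up to 0.5. Nor does section 4.4 say whether 0.7 is the SD of the level or of the change. With a change SD of 0.6, power at 20% loss is 88.9%, 81.0%, 66.5% and 51.2%. With 0.8 it is below 80% throughout, but so is the observed-data analysis (69.2% with 32 per arm). All of this stands as a limit on the power figures. None of it affects the shrinkage.

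Several narrower points also stand as qualifications:

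- If baseline were the preoperative sample, the estimate would shrink equally but the power figures would change, because imputed changes would then vary. With an assumed SD of 0.5 for the surgical drop, power at 20% loss is 73.9%, 67.0%, 55.9% and 44.5%.
- Section 9.6 does not address a woman who misses week 3 but attends week 6. Carrying forward is the usual reading and not the only possible one.
- At week 6, a woman seen at week 3 carries a post-treatment value, so this mechanism does not apply to her. Nothing here is quantified for week 6.
- The 10% against 20% imbalance is illustrative. Blinding makes differential loss less likely, although the different side-effect profiles in sections 6.3 and 12.2 leave it possible.
- A repeated-measures model with baseline as a covariate omits women with no post-treatment value. Under missing at random this does not bias the contrast, and multiple imputation would retain them.

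**Conclusion.** The concern holds. It follows from the plan's own schedule and rule that a retained woman without a week-3 sample is scored at a pre-treatment level. Under equal, non-informative loss the week-3 difference is underestimated by exactly the imputed fraction, up to 0.10 of the 0.50 mmol/L the protocol calls clinically important if the full 20% is lost early and kept in the analysis. Confidence in this part is high.

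That power can fall below 80% is also established, but how far depends on the rise, the SD of change, the timing of loss and the share withdrawing consent. With all of a 20% loss early and imputed, and an SD of 0.7, power is below 80% at every rise tried, though only just if the comparator does not rise. Bias in either direction and an inflated type I error require unequal loss together with a general rise. The plan should be changed before analysis; the design and sample size need not be.

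**What to change.** In section 9.6, with matching wording in 9.1 and 9.3:

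1. Replace last-observation imputation as the primary method with a likelihood-based repeated-measures model of all observed week-3 and week-6 hemoglobin: treatment, visit, treatment-by-visit and baseline hemoglobin, with unstructured covariance. Report the contrasts at the time points already named. Alternatively, extend the multiple imputation already planned in 9.6 to hemoglobin, using the other visits and baseline variables. That is the smaller edit and keeps women with no post-treatment sample.
2. Define baseline as the day-1 pre-treatment hemoglobin.
3. If covariates are added, use only minimisation factors from section 7.2 that vary in women having a caesarean section.
4. Add a sensitivity analysis for data not missing at random, for example a shift applied to the imputed values by arm over a stated range. Keep last-observation imputation at most as a further sensitivity analysis.

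The cost is wording in three sections and a little more analysis, with no extra patients, visits or samples. The new primary method assumes data are missing at random, and item 4 probes that assumption.
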